- 2) **Patient-Reported Opioid Use** at three months. This will be collected using a customized instrument assessing whether participants have taken any opioid medication in the last 24 hours. The 24-hour timeframe was selected to maximize accuracy in patient recall and has been used previously. In brief, opioid medications are listed by brand and generic names; a “yes” response to any medication triggers an additional query asking the participant to specify the medication dose (e.g., oxycodone 10mg) and quantity (e.g., four pills), allowing for standardization by morphine milligram equivalents (MME). We anticipate treating this variable as either count or a binary (any dose vs. none), or continuous (MME) for analyses.

Exploratory Outcomes

We expect the following outcomes to be related to the primary and the major secondary outcomes of interest. We deem the more exploratory in nature, and they thus carry less weight in analyses and overall inferences regarding efficacy of intervention.

- 1) **Opioid Prescription Filling** will be queried in the state prescription monitoring database. We anticipate treating this variable as count, binary, or continuous (MME).
- 2) **Patient-Reported Prescription Analgesic Use** in the last 24 hours will be collected using the same customized instrument described above for opioid use. Prescription analgesics include: opioids, benzodiazepines, skeletal muscle relaxants, and gabapentinoids. We anticipate treating this variable as either count or binary.
- 3) **Prescription Analgesic Filling** will be queried in the state prescription monitoring database. Prescription analgesics include: opioids, benzodiazepines, skeletal muscle relaxants, and gabapentinoids. We anticipate treating this variable as either count or binary.
- 4) **Numeric Pain Rating Scale (NPRS)** measures pain intensity from 0 to 10 and is easily understood by laypersons, clinicians, and researchers. We will assess a single item relating to average pain intensity over the last 24 hours. We plan to treat this as a continuous outcome, but we anticipate requiring transformation or nonparametric analyses, as this variable will likely be skewed and exhibit flooring / ceiling effects.

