In addition to repeating the above analyses with exploratory outcomes, we will conduct exploratory analyses to study effects among subgroups of patients (moderator analyses) and examine the potential impact of PT use among patients in the control arm.

Planned moderator analyses will include the following moderators:

1. Opioid naivete as measured by whether patients report taking opioids within the last 24 hours at their index ED visit or have a history of opioid prescription filling in the Illinois prescription monitoring program within the last 3 months.
2. Initial symptom burden measured as “moderate/severe” if their baseline measures of PROMIS pain scores are ≥ 60 or their STarT score registers as “high risk,” defined as a subscore ≥ 4 (questions 5-9).
3. Age ≥ 65 years old
4. Primary treatment classification, as per the clinical care protocol (directional preference, traction, stabilization, manipulation, nociplastic presentation). As primary treatment classification is assigned only in those participants in the treatment arm (NEED-PT), we will use two approaches to study the effects of treatment classification. First, we will modify GLMM to include treatment classification effects (as opposed to just a study arm effect). Second, we will use matching methods (e.g., propensity score matching or augmented synthetic controls) to match individuals in the NEED-PT arm who have a given primary treatment classification to control arm participants on baseline covariates. We would then use GLMM to estimate the impact of each treatment classification separately.

Analyses will focus on PROMIS-PI scores measured three months after patients’ index visits, as well as ODI scores and opioid use (proportion using an opioid within the last 24 hours) at the same time point. Analyses will involve generalized linear models with appropriate link functions (identity for PROMIS-PI and logit for opioid

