use) that include fixed effects for baseline measures of the outcome of interest, treatment assignment, a moderator variable, and a treatment-moderator interaction. As above, PROMIS-PI will be modeled with standard normality assumptions, which will be evaluated via residual diagnostics and appropriate transformations will be used as necessary. Separate models will be fit for each outcome and moderator. Tests for the treatment-moderator interaction will be two-sided with a 5% type I error rate, and we will report point estimates and 95% confidence intervals. For the logistic regression involving opioid use, we will use Wald confidence intervals and Wald tests. We will not make multiple comparison adjustments.

Mediation analyses will focus on PCS and PSEQ as possible mediators. Our hypotheses are that embedding a PT in the ED can impact patients downstream pain catastrophizing and self-efficacy which will in turn lead to lower reported pain and less frequent opioid use. Our key dependent variables will be PROMIS-PI and opioid use at three months after the index visit. PCS and PSEQ measured at one month will be the mediators of interest. We will use a nonparametric approach to analyses, running separate models for each outcome and mediator (5). In addition, we will examine the possible correlation between mechanisms by using a joint nonparametric estimation framework (6).

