8. POWER AND SAMPLE SIZE CONSIDERATIONS

Power calculations focus on the primary endpoint of PROMIS-PI at three months, and we desire adequate (at least 80%) power to detect the minimum clinically important PROMIS-PI score difference of 3.5-5.5 points as previous literature suggests (8). If we assume a standard deviation of 10 points, which is the defined standard deviation of PROMIS-PI, this corresponds to a desired minimal detectable effect size of $d=0.35$ standard deviation unit difference across arms. Power considerations also account for a 20% drop-out rate for physician clusters (e.g., physician leaves the practice or refuses participation after randomization) and a 20% lost to follow-up rate among recruited participants. We used “The Shiny CRT Calculator” to explore varying assumptions on cluster size (i.e., average number of participants per physician), number of clusters/physicians, and ICC. Under the parallel-arm, “cohort” design, with baseline measurement of primary outcome (PROMIS), the calculator also allows for an assumption on correlation between baseline and follow-up. The table below illustrates power to detect at least a 3.5 mean difference across study arms if we assume just two time points (baseline and three months, which we deem conservative as we will have up to seven time points of observation, including baseline) per participant with a correlation between the two of approximately 0.50. We conservatively estimate that we will need to enroll up to 360 total participants to account for worst-case (20%) scenario dropout for both physicians and participants. **Thus, after accounting for physician and participant dropout, a final sample size of 16 physicians per arm and 7 participants per physician (n=224 total or 112 per arm) achieves 84% power** to detect a mean between-arm difference of 3.5 PROMIS-PI points assuming standard deviation of 10 points, ICC of 0.10, and a two-sided 5% level of significance. In our pilot work, we found a small ICC (0.01-0.04), indicating minimal within-physician effects that were not significant; however, we utilize a more conservative estimate of the ICC at 0.10 in the event that greater than anticipated within-physician effects are encountered. In the event that ICC is lower than expected or dropout rate is lower than 20%, we anticipate often over 90% to detect a meaningful difference across arms. Similar effect size in secondary outcomes (e.g., 0.35 standard deviation units difference in ODI across arms) are also detectable with at least 80% power under similar assumptions. Additionally, we plan to conduct secondary longitudinal analyses involving multiple time points per participant (i.e., more data observations) using likelihood-based methods that are robust to missing data. Therefore, we anticipate adequate power to evaluate differences across arms in outcome trajectories. **Since our target final analytic sample size is 224 total participants, if we can reach our target with fewer participants enrolled than 360, we will consider stopping enrollment.** We will plan to monitor dropout rates, ICC, standard deviation, and within-participant correlation

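### The SAP fixes Wald inference for the exploratory opioid-use moderator models and gives no rule for an empty arm-by-moderator cell, where a Wald test cannot detect any interaction

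*SAP*

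**What the plan says.** SAP section 6, under Exploratory Analyses, plans moderator analyses of three outcomes at three months. One is "opioid use (proportion using an opioid within the last 24 hours) at the same time point". Each model contains the baseline value of the outcome, "treatment assignment, a moderator variable, and a treatment-moderator interaction". On inference the section says "Tests for the treatment-moderator interaction will be two-sided with a 5% type I error rate", promises point estimates with 95% confidence intervals, and then adds: "For the logistic regression involving opioid use, we will use Wald confidence intervals and Wald tests".

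Three moderators are binary: opioid naivete, initial symptom burden, and "Age ≥ 65 years old". The fourth, primary treatment classification, is assigned only in the NEED-PT arm and is handled by other methods, so it is outside this point.

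The moderator text has no rule for empty or sparse cells; its remark about transformations concerns PROMIS-PI. Three clauses elsewhere could bear on the matter:

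- Section 6 says generally that the team will consider transformation, nonparametric or exact methods when assumptions are violated.
- Section 6 also says that if binary or count mixed models are unstable, the physician random effect is expected to give way to a participant random effect.
- Section 9 allows the SAP to be updated for unexpected outcome distributions.

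The SAP gives no expected opioid-use rate and no expected stratum size.

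**The concern.** With a binary moderator, the arm, moderator and interaction terms saturate four cells. If one cell has no opioid users, the likelihood keeps rising as the interaction coefficient moves towards infinity (quasi-complete separation). Software stops at an arbitrary large value with a huge standard error, so the Wald statistic falls to about zero. Adjusting for baseline use does not remove this, because every patient in that cell still has the same outcome.

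The prespecified rule would therefore return p close to 1 and a meaningless interval for the most extreme pattern the data can show: no opioid use in one arm of a stratum. A reader could take that for evidence against effect modification. The outcome covers a single 24-hour window and one stratum may be small, so the situation is not far-fetched.

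**Working it through.** **Inputs from the SAP.** Section 8: "a final sample size of 16 physicians per arm and 7 participants per physician (n=224 total or 112 per arm) achieves 84% power", i.e. 16 × 7 = 112 per arm after the assumed dropout. Maximum enrolment is 360, or 180 per arm before dropout. Outcome (section 2): a customized instrument "assessing whether participants have taken any opioid medication in the last 24 hours".

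**Inputs assumed.** Opioid use p (5% to 20%) and the smaller stratum's share (mainly 20%), because the SAP gives neither.

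**The plan's own figure.** The 84% power is for PROMIS-PI; none is stated for these models. With design effect 1 + 6 × 0.10 = 1.6, r = (7 × 0.10 + 0.90 × 0.50)/1.6 = 0.719 (cluster autocorrelation taken as 1), and variance 2 × 100/112 × 1.6 × (1 − 0.719²) = 1.38, power is Φ(3.5/1.175 − 1.96) = 84.6%, so the figure reproduces. It matters here only as the source of 112 per arm.

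**Step 1: what Wald does with an empty cell.** Illustrative table: age 65 or over, 6/22 control and 0/22 NEED-PT; under 65, 9/90 in each arm. The logistic model has arm, moderator and interaction, without baseline covariate or clustering.

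| Method | Interaction (log odds ratio) | p |
|---|---|---|
| Wald (maximum likelihood) | −22.6, SE 16,941 | 0.999 |
| Likelihood ratio | diverges | 0.006 |
| Firth, penalized profile likelihood | −2.88 | 0.020 |

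The Wald 95% interval is −22.6 ± 1.96 × 16,941, about −33,000 to +33,000. In five other tables with an empty cell, Wald p was 0.998 to 0.999 each time, while the likelihood-ratio p ranged from 0.0006 to 0.25. The Wald result carries no information about which of these tables was observed.

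**Step 2: one event instead of none.** With 1/22 in place of 0/22 in the table above, Wald p = 0.095 against 0.061 for likelihood ratio. In another table (control 10/90 and 8/22; NEED-PT 12/90 and 1/22), Wald p = 0.026 against 0.009. Wald is conservative here, but it does not collapse.

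**Step 3: how often a cell would be empty.** With n patients per arm in the smaller stratum and equal use p in both arms,

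P(at least one empty cell in the stratum) = 1 − [1 − (1 − p)^n]².

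- 112 per arm, 20% stratum (n = 22), p = 10%: 0.90^22 = 0.098, giving 1 − 0.902² = 19%.
- Same, p = 5%: 0.95^22 = 0.324, giving 54%.
- Same, p = 20%: 1.5%.
- 112 per arm, 25% stratum (n = 28), p = 15%: 2%.
- 112 per arm, 10% stratum (n = 11), p = 5%: 81%.
- 180 per arm, 20% stratum (n = 36), p = 10%: 0.90^36 = 0.0225, giving 4.5%.
- Same, p = 5%: 0.95^36 = 0.158, giving 29%.

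**Step 4: effect on the test.** Simulation with cells of 90 and 22 per arm, no covariates or clustering. With a strong assumed interaction (27% control against 3% NEED-PT in the small stratum, 10% elsewhere), Wald rejects in about 12% to 13% of runs, Firth in about 47% and plain likelihood ratio in about 62%. With no interaction and 5% to 10% use, Wald rejects in 1% or less, Firth in about 2% to 5% and likelihood ratio in about 7%. Against the nominal 5%, Wald is far too conservative and plain likelihood ratio is somewhat liberal.

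**The case against.** Wald inference is an ordinary prespecified choice, and the analyses are labelled exploratory. The general clauses in sections 6 and 9 let the team move to exact or other methods, and a competent analyst would not publish a standard error near 17,000. That stands in part: Wald is not strictly binding. But those clauses are discretionary, contain no trigger for empty cells, and would be invoked after the data are seen. Swapping one random effect for another does not cure separation.

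A reader might infer that empty cells are likely in this trial. The SAP does not support that. It gives neither an event rate nor a stratum size, and the assumed scenarios run from about 1.5% to 81%. The 112 per arm is also the worst-case analytic sample, and the risk falls as the sample grows.

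A reader might also infer that near-empty cells fail in the same way; step 2 shows that they do not.

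Nor does every empty cell hide a finding. When use is equal across cells, the joint chance of an empty cell and a likelihood-ratio p below 0.05 was about 6% at 5% or 10% use with a 20% stratum, and those would be false positives. The larger loss in step 4 depends on a strong real interaction, which is itself an assumption.

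**Conclusion.** The point holds as a conditional defect. If an arm-by-moderator cell has no opioid users, the stated Wald rule gives p of about 1 and an interval without content, whatever the strength of the interaction. With few events it is conservative to a much smaller degree. Under equal use and a 20% stratum, the chance of an empty cell in that stratum is about 19% (10% use) or 54% (5% use) at 112 per arm, and 4.5% or 29% at 180 per arm. It is small at higher use or, unless use is rare, with larger strata. These figures rest on assumed rates and ignore clustering.

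Only one outcome in the exploratory moderator analyses is touched, for the three binary moderators. The primary analysis, the main opioid comparison and the PROMIS-PI and ODI moderator models are unaffected. The priority is low, but the change costs almost nothing.

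**What to change.** In SAP section 6, Exploratory Analyses, replace the sentence prescribing Wald intervals and tests with: for opioid use, the treatment-moderator interaction will be estimated by Firth-penalized logistic regression, with penalized profile-likelihood tests and 95% confidence intervals; the number of events and patients in each arm-by-moderator cell will be shown beside each result.

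Do not add a minimum-event rule that replaces the test by counts alone. It would remove the test in exactly the tables where Wald fails.

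The cost is one sentence, with standard SAS or R methods. The estimates are mildly shrunk, and the test remains somewhat conservative when events are very few. The moderator models are described as generalized linear models and list no random effect, so the replacement fits them as written.

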7. ANALYTIC DATASET

Primary and secondary outcomes will be evaluated across arms under a modified intention-to-treat (mITT) principle, (1) whereby all participants will be included in analyses, regardless of their or their physicians' adherence to their assigned study arm, and (2) only participants contributing at least one follow-up data point will be included. That is, we will exclude patients who are lost to follow-up before Week 1. Sensitivity analyses will be detailed after data collection; however, we plan to conduct sensitivity analyses that would involve:

- 1) Excluding patients who are ultimately admitted to the hospital after their ED visit. We anticipate that the number of participants meeting the criteria for this sensitivity analysis will be low. If $n \leq 10$ participants, we will combine with sensitivity analysis #2 to create a single sensitivity analysis.
- 2) Excluding patients with an alternative diagnosis after enrollment that would have deemed them otherwise ineligible (e.g., discovery of kidney stones or shingles after enrollment). We anticipate that the number of participants meeting the criteria for this sensitivity analysis will be low. If $n \leq 10$ participants, we will combine with sensitivity analysis #1 to create a single sensitivity analysis.
- 3) Excluding patients who cross over to the study arm to which they were not assigned (i.e., per-protocol analysis). If this occurs frequently, we may explore instrumental variables or propensity score methods as sensitivity analyses. This per-protocol analysis is also described in the previous section as a "complier analysis." We clarify that these two descriptions refer to the same single analysis.

Power and sample size considerations allowed for some missing data (20%). Any analysis involving missing data inherently makes assumptions about why data are missing and such assumptions are often not testable, nor are the missing data mechanisms to which they pertain necessarily known prior to the completion of data collection. Thus, we will evaluate potential missingness mechanisms and patterns that will ultimately inform multiple analyses, but we highlight here our anticipated steps and delineate possible primary and sensitivity analyses.

We will examine rates of missing data for all variables and determine whether the rates vary by participant characteristics and study arm. These summarizations will inform potential biases resulting from missing data.

Given that the mechanism of missing data may not be explicitly known in many cases, we plan to present multiple analyses conducted under various assumptions of missingness. Mixed effects models planned for longitudinal analysis are generally robust for unbalanced data across study time points, and so we will present analyses that ignore missing observations, which assumes that they are missing completely at random (MCAR). Additional analyses may be explored to evaluate overall robustness of inferences should greater than 10% of data wind up missing. These analyses will again serve as sensitivity analyses and provide inference under different assumptions regarding missingness. The details of these analyses will be documented at the time of analyses (if needed). We now specify the following additional analyses:

- 4) Multiple Imputation (MI) for mITT analyses will involve the imputation of missing follow-up data among the modified intention to treat population. This approach assumes data are missing at random (MAR, a less stringent assumption), as opposed to MCAR (more stringent). We will use multilevel imputation models to generate $m=40$ imputations using observed data in our mITT population (i.e., those participants providing follow-up data at least one timepoint). This will allow us to confirm the robustness of our primary mITT analysis to the assumption of MAR vs. MCAR data.
- 5) ITT analysis: Because the mITT population excludes participants lost to follow-up (LTFU) (i.e., excludes those participants who provided follow-up data at zero of the possible timepoints), we will conduct a sensitivity analysis using data on all eligible patient participants (i.e., including those participants who provided zero follow-up data) and combining MI with inverse probability weighting (IPW).⁽⁷⁾ The probability of *not* being LTFU was estimated as a function of baseline characteristics and baseline measures of outcomes using a logistic regression model. Then, among our mITT imputations, GLMMs will be estimated using weights inversely proportional to that probability. This method adjusts analyses for differences between the LTFU and mITT populations and provides a measure of how sensitive mITT analyses are to excluding LTFU patient participants.

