6. STATISTICAL METHODS

We plan to use descriptive statistics to summarize baseline patient and physician-level variables both overall and by arm. We will use mean±standard deviation (or median and interquartile range [IQR] as appropriate) for continuous variables and frequency / percentage for categorical variables. Specifically, we will summarize age, sex, Keele STarT score, baseline patient-reported outcome scores (PROMIS-PI and ODI), analgesic medication prescription at ED discharge, and the variables listed above. Analyses will involve normal theory methods in general, and in cases of violations of assumptions, we will consider transformation and / or nonparametric / exact methods as appropriate.

Analyses will assume a two-sided 5% significance level. All primary efficacy and safety analyses will be pre-specified as outlined in this SAP, and deviations from planned analyses or post hoc analyses will be labeled as such in any reports or dissemination materials. We do not plan to control for multiple hypothesis tests.

In analyses for each outcome, we plan to control for the respective outcome value at baseline (i.e., in an analysis of covariance [ANCOVA] approach). Analyses for the primary outcome (Y) will involve a linear mixed model (LMM) with repeated measures with fixed effects for: study arm, baseline outcome score (Y0), timepoint, timepoint-by-arm interaction, and known influential predictor effects (age, sex, Keele STarT score). Inference will focus on treatment impacts for the outcome at three months. We will include a random physician effect to account for both within and between physician variability and also to allow for estimation of the intra-cluster correlation coefficient (ICC). The repeated measures on the same participant over time will also introduce a correlation structure across time points, providing the justification for modeling the correlation structure at the

participant level over time. We will use an unstructured correlation matrix to account for the repeated measures within a participant as this has the least assumptions. If the model does not converge or parameters cannot be estimated under this unstructured covariance pattern, we will explore simpler covariance patterns using residual estimated maximum likelihood (REML) comparisons. Including repeated measures per participant will allow us to make most use of all participant data after baseline. We will use assume an unstructured covariance across time.

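### SAP Section 7 labels the primary mixed model an MCAR analysis and gives multiple imputation the job of checking MAR versus MCAR, but both rest on MAR and no specified analysis relaxes it

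*SAP*

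**What the plan says.** Section 6 (Statistical Methods) sets the primary model as a linear mixed model with fixed effects for "study arm, baseline outcome score (Y0), timepoint, timepoint-by-arm interaction, and known influential predictor effects" (age, sex, STarT score), a random physician effect and an unstructured within-participant covariance. On the use of data it says: "Including repeated measures per participant will allow us to make most use of all participant data after baseline". The same section calls the strategy robust to incomplete data. Section 8 describes the longitudinal analyses as likelihood-based and robust to missing data.

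Section 7 (Analytic Dataset) states the aim: "we plan to present multiple analyses conducted under various assumptions of missingness". It then says of the mixed models: "we will present analyses that ignore missing observations, which assumes that they are missing completely at random (MCAR". Sensitivity analysis 4 is multilevel MI with 40 imputations in the mITT population, labelled as the less stringent MAR analysis. Its purpose is given as: "This will allow us to confirm the robustness of our primary mITT analysis to the assumption of MAR vs. MCAR data".

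Sensitivity analysis 5 brings in participants with no follow-up through a logistic model on baseline variables: "Then, among our mITT imputations, GLMMs will be estimated using weights inversely proportional to that probability".

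Anything further is conditional: "Additional analyses may be explored to evaluate overall robustness of inferences should greater than 10% of data wind up missing". On its content: "The details of these analyses will be documented at the time of analyses (if needed".

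**The concern.** MCAR is the assumption of a weaker analysis than the one Section 6 describes. A correctly specified likelihood-based model that uses every observed visit is valid when missingness depends on arm, model covariates and outcomes already observed, which is MAR. If the primary model and MI share that assumption, comparing them cannot do the job Section 7 gives it.

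Two misreadings could follow. Close agreement could be taken as reassurance about missing data in general, although it carries no information on departures from MAR. A gap could be taken as failure of MCAR, although it may come from the mixed model's specification (Section 6 has one baseline slope for all visits) or from auxiliary variables in the imputation model. Sections 7 and 8 allow for 20% missing data, so the question is a practical one.

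**Working it through.** **1. What each specified analysis assumes**

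| Analysis | SAP label | Assumption it needs |
|---|---|---|
| Primary mixed model (Section 6) | MCAR | MAR, if correctly specified |
| Analysis 4, MI | MAR | MAR |
| Analysis 5, MI plus weighting on baseline variables | none given | MAR |
| Clause for more than 10% missing | none given | no method named |

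**2. Does the mixed model need MCAR?** Two simulations were run. Their variances, slopes and dropout rules are assumptions, so the pattern counts and the sizes do not.

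*First simulation.* 200 trials per case; 32 physicians with 9 participants each; visits at Week 1 and Months 1 to 3; SD 10; ICC 0.04. MAR dropout depends on the previous score, in opposite directions by arm, and is deliberately strong (17% missing at Month 3). MCAR dropout is 20%. Age, sex and STarT score are omitted. Mean Month 3 effects:

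| Case | Full data | Complete-case ANCOVA | Mixed model, one baseline slope | Mixed model, baseline-by-visit | MI | Mean absolute gap, one-slope model and MI |
|---|---|---|---|---|---|---|
| Constant slope, MAR | -3.49 | -4.74 | -3.53 | -3.53 | -3.53 | 0.09 |
| Slope falling 0.7 to 0.3, MAR | -3.48 | -4.75 | -2.85 | -3.53 | -3.53 | 0.70 |
| Falling slope, MCAR | -3.48 | -3.57 | -3.51 | -3.53 | -3.52 | 0.32 |
| Constant slope, MCAR | -3.49 | -3.56 | -3.53 | -3.53 | -3.52 | 0.07 |

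- Row 1: dropout is not MCAR, complete-case analysis is off, and the correctly specified mixed model is not.
- Row 2: the gap from MI closes once baseline-by-visit terms are added, so it comes from specification.
- Row 3: MCAR holds, yet a single trial shows a gap of 0.32 points on average (0.06 with baseline-by-visit terms).

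*Second simulation.* 40 physicians with 9 participants each, different variances, about 35% missing under MAR and MNAR. Mixed-model bias against full data was 0.00 under MCAR, -0.02 under MAR (Monte Carlo SE 0.02) and +4.3 under MNAR. MI bias under MNAR was +4.4. The REML mixed model and MI differed by only 0.06 to 0.07 points on average in every scenario, so they agree closely even when both are badly wrong.

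**3. The plan's own precision.** Inputs from Section 8: 112 per arm, 7 per physician, SD 10, ICC 0.10, baseline correlation 0.50, difference 3.5. Assumption not in the SAP: cluster autocorrelation of 1.

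- Design effect = 1 + 6 × 0.10 = 1.6.
- r = (7 × 0.10 + 0.90 × 0.50)/1.6 = 0.719, so 1 − r² = 0.483.
- Variance = (2 × 100/112) × 1.6 × 0.483 = 1.38, so SE = 1.18.
- Power = Φ(3.5/1.175 − 1.96) = 84.6%, against the stated 84%.

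Working back from 84%: SE = 3.5/(1.960 + 0.994) = 1.185. The significance limit is 1.96 × 1.185 = 2.32.

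**4. How far from MAR before a result changes?** If missing Month 3 values in one arm are shifted against the treatment by δ, the difference moves by f × δ, where f is the fraction missing in that arm. Holding the SE fixed, the tipping point is (estimate − 2.32)/f.

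| Estimate | f = 0.20 | f = 0.10 |
|---|---|---|
| 3.5 | 5.9 | 11.8 |
| 3.0 | 3.4 | 6.8 |
| 2.5 | 0.9 | 1.8 |

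For a true effect of 3.5, the share of trials that are significant yet tip at δ or less is P(2.32 < estimate < 2.32 + fδ):

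- f = 0.20: δ = 3.5 gives an upper limit of 3.02 and 18%; δ = 5.5 gives 3.42 and 31%.
- f = 0.10: δ = 3.5 gives 2.67 and 8%; δ = 5.5 gives 2.87 and 14%.

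Equal shifts in both arms with equal missingness cancel.

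**The case against.** The strongest reply is that the mixed model as written may in fact need MCAR. In the falling-slope case it is right on average under MCAR (-3.51) and wrong under MAR (-2.85), while MI is right under both. That stands, but only for a misspecified model. It makes MI a check on specification, which is useful and is not the purpose stated. One trial also gives one gap, and row 3 shows that gaps arise when MCAR holds. So a reader should not infer that analysis 4 is worthless.

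A reader might also infer that the sponsor would report agreement as settling the missingness mechanism. The SAP does not say so: Section 7 states that such assumptions are often untestable and speaks only of the robustness of the primary analysis.

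Nor does the SAP establish that any later analysis beyond MAR must be called post hoc. Section 6 requires that label for unplanned analyses, but Section 7 leaves room for further sensitivity analyses and Section 9 provides for SAP updates. The status of such an analysis is arguable.

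Finally, the sizes rest on choices. The slope and dropout pattern are assumed, a shift in one arm only is unfavourable, and an MCID does not measure how far unseen values depart from MAR. All of this stands, and the figures are offered as illustration only.

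**Conclusion.** The point holds. The MCAR label is wrong for the model in Section 6, the stated purpose of analysis 4 does not follow, and everything specified rests on MAR despite the promise of varied assumptions. Version 2.0 was written partly to specify the missing-data approach, so the gap lies within what this document set out to fix.

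A reader might infer that the primary result is biased or underpowered. It is not shown to be: the label understates the model's validity and leaves estimator, population and power unchanged.

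The size is moderate. With SE 1.18 and 20% missing in one arm, a 3.5-point result is fairly robust (tipping at 5.9 points), while results nearer the significance limit are not (3.4 points for an estimate of 3.0; 0.9 for 2.5). This assumes a fixed SE and a shift in one arm only. The 20% is the SAP's overall allowance; mITT excludes participants with no follow-up, so the missing fraction there may be lower, which is why 10% is also shown. The change should be made, but the primary analysis does not depend on it.

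**What to change.** 1. Reword Section 7. State that the primary mixed model assumes MAR given arm, covariates and observed outcomes. Delete the MAR-versus-MCAR purpose. Describe analysis 4 as a check on specification and auxiliary information under MAR, with a gap prompting a look at the mixed model (for example, baseline-by-visit terms). Describe analysis 5 as a MAR analysis that addresses the mITT exclusion.

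2. Before database lock, specify an arm-specific delta-adjusted tipping-point analysis of Month 3 PROMIS-PI on the 40 mITT imputations, and report the shift at which the conclusion changes. State that it shows sensitivity to departures from MAR and does not test for them. Extending it to participants with no follow-up is optional, because it needs imputation that analysis 5's weighting does not supply. If the analysis is first specified after lock, say so in the report.

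Cost: some SAP wording, one extra table and a small amount of analysis work. Sample size and the primary analysis do not change.
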